## **Inclusion and exclusion criteria**

### ***Inclusion criteria***

1. Male and female patients aged 18-75 years old.
2. Diagnosis of new coronavirus infection COVID-19 based on medical examination: axillary temperature  $>37.5^{\circ}\text{C}$ , symptoms of upper respiratory infection,  $\text{SpO}_2 \geq 95\%$ , no symptoms of moderate or severe levels.
3. The minimal baseline score for COVID-19-related symptoms defined as follows: at least two symptoms with a score of 2 or higher, with the exception of taste and smell where subjects may have a score of 1 or higher, and the absence of shortness of breath (difficulty breathing).
4. Positive rapid test for SARS-CoV-2 (COVID-19).
5. The first 24 hours from the disease onset.
6. Patients giving their consent to use reliable contraception during the study.
7. Signed patient information sheet (informed consent form).

### ***Exclusion criteria***

1. Moderate and severe COVID-19.
2. The first four weeks after any vaccination/revaccination, including against COVID-19, influenza, pneumococcal and other infections.

3. Suspected pneumonia, bacterial infection (including otitis media, sinusitis, urinary tract infection, meningitis, sepsis, etc.).
4. Patients requiring medications prohibited within the study.
5. Medical history or previously diagnosed primary and secondary immunodeficiency.
6. Medical history/suspicion of oncology of any localization (except for benign neoplasms).
7. Exacerbation or decompensation of chronic diseases affecting the patient's ability to participate in the clinical study.
8. Malabsorption syndrome, including congenital or acquired lactase or disaccharidase deficiency, galactosemia.
9. Allergy/hypersensitivity to any of the components of the medications used in the treatment.
10. Pregnancy, breast-feeding; childbirth less than 3 months prior to the inclusion in the trial, unwillingness to use contraceptive methods during the study.
11. Use of medications listed in "Prohibited concomitant therapy" within 4 weeks before the study entry.
12. Patients who, from the investigator's point of view, will fail to comply with the observation requirements of the trial or with the intake regimen of the study drugs.
13. Medical history of mental diseases, alcoholism or drug abuse which, according to the investigator's opinion, will interfere with the study procedures.
14. Participation in other clinical trials within 3 months prior to enrollment in this study.
15. The patient is related to the study center staff directly involved in the trial or is the immediate family member of the investigator. Immediate family is defined as a spouse, parents, children or siblings, whether natural or adopted.
16. The patient works for OOO "NPF "MATERIA MEDICA HOLDING" i.e. is the company's employee, part-time employee under contract or appointed official in charge of the trial, or their immediate family.

### **Criteria for Withdrawal or Termination**

1. Screening failure.
2. Negative PCR test for SARS-CoV-2.
3. Failure or refusal of the patient to follow the protocol.
4. Deviation from personal visit schedule by more than 1 day.
5. The necessity to use medications not permitted in the study.
6. An adverse event requiring discontinuation of the study drug.
7. Patient's decision to withdraw early for lack of efficacy or other reasons.
8. Pregnancy.

9. Cases not stipulated in the protocol where the investigator decides that further participation may harm the patient.
10. Eligibility error.
11. Participation in any other clinical study.
12. Unblinding.

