During the study, six visits are planned: on days 1, 3, 6, 10, 21, and 28 (visits 1, 2, 3, 4, 5, and 6). Visits 1, 3, and 4 are in person (visits to the patient or visits to the medical center) when the physician examines the patient and monitors EPD records. At visit 3, the patient's adherence to treatment is assessed and laboratory tests are performed. Visits 2, 5 and 6 are phone surveys to determine the patient's condition, presence/absence of complaints. In case of worsening of disease duration, the physician makes an extra visit. Patients with COVID-19 progression to more severe level as well as hospitalized patients are considered as reaching the study endpoints and terminate participation in the study ahead of schedule. The therapeutic approach is determined by the current edition of the clinical recommendations of the Ministry of Health of the Russian Federation «Prevention, diagnosis and treatment of a new coronavirus infection (COVID-19)».

During the study, the use of paracetamol and medicines for the treatment of concomitant diseases is allowed, with the exception of the drugs specified in the section «Prohibited concomitant treatment».

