## Study design scheme

## Schedule of study procedures

Procedure/Visit	Visit 1 (Day 1)	Visit 2* (Day 3)	Visit 3 (Day 6)	Visit 4 (Day 10)	Visit 5* (Day 21±1)	Visit 6* (Day 28±1)	Unscheduled visit**
Informed consent	+						
Registration of a study patient in the IVRS  and assignment of patient ID	+						
Complaints collection	+	+	+	+	+	+	+
Medical history	+						
Demographic data (gender and year of birth of the patient)	+						
Physical examination	+		+	+			+
Thermometry	+		+	+			+
Evaluation of 14 Symptoms Associated with COVID-19	+		+	+			+
SARS-CoV-2 rapid test	+						
Nasopharyngeal swabs for PCR	+		+	+			
Pulsoxymetry (SpO 2 )	+		+	+			+
Electronic patient diary	+	+	+	+	+	+	+
Concomitant diseases and conditions	+	+	+	+	+	+	+
Concomitant therapy	+	+	+	+	+	+	+

Procedure/Visit	Visit 1 (Day 1)	Visit 2* (Day 3)	Visit 3 (Day 6)	Visit 4 (Day 10)	Visit 5* (Day 21±1)	Visit 6* (Day 28±1)	Unscheduled visit**
Pregnancy test	+						
Inclusion/exclusion criteria	+						
Laboratory tests*** (for safety evaluation)	+		+				+****
Randomization	+						
Study drug supply	+						
Antipyretic drug and thermometer supply	+						
Study drug accountability and return			+				+****
Treatment compliance			+				+****
Safety evaluation	+	+	+	+	+	+	+
Visit completion	+	+	+	+	+	+	+
Study completion*****						+	+

 Interactive Voice Responsible System with Web Access

\* Phone survey

\*\* Unscheduled visit will be performed in case of aggravation (based on EPD), at the investigator's discretion and in case of early withdrawal (e.g. at the patient's option).

\*\*\* Include complete blood analysis and urinalysis, serum chemistry (total protein, total bilirubin, creatinine, ALT, AST, cholesterol, C-reactive protein). Performed with availability of signed PIS and ICF including the patient's consent for blood and urine sampling.

\*\*\*\* If unscheduled visit is made before visit 3.

\*\*\*\*\* In case of early withdrawal the procedure may be carried out at Visits 1-5 or at uncheduled visit.

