### Samples

*Total set:* all patients who have signed ICF. This sample will consider all the recorded AEs, including those occurred prior to the study therapy.

*Safety population:* all included and randomized patients who received at least one dose of the study drug. This sample will be used for **analysis of the study treatment safety and tolerability**, as all adverse events identified after the study drug administration will be recorded.

*Full Analysis Set.* This sample includes all enrolled patients, except for those who met at least one of the following events:

- 1) non-compliance with inclusion / exclusion criteria;
- 2) patient did not take a single dose of the study drug;
- 3) lack of any data about the patient after administration of the study drug.

This sample, the most consistent with the “Intention-to-treat” principle, will be used for the **Intention-to-treat analysis (ITT analysis)** of the study therapy efficacy.

 Holder of license: OOO “NPF “MATERIA MEDICA HOLDING”, No. 70100045.

*Per protocol set.* This sample includes all patients who completed the therapy as per the study protocol and completed all the scheduled visits. This set will be used for the ***Per Protocol analysis (PP analysis)*** of the study therapy efficacy. *PP set* will not include the patients with their data completely or partially invalid for analysis due to a protocol deviation.

The list of deviations that may result in complete or partial invalidity of data is developed by a medical expert jointly with a biostatistician according to the study design.

The deviations that may result in partial or complete invalidation of the study subject's data.

1. Inappropriate distribution/supply of the study drug.
2. Prescription of prohibited therapy.
3. Increase or decrease in the study drug dosing by  $\geq 25\%$ .
4. Inability to assess the patient's compliance using the formula (e.g. loss of pack with the product).
5. Major discrepancies between source documents and CRF identified during monitoring or another authorized inspection.
6. Violation of the procedure of obtaining informed consent.
7. Non-compliance with the clinical study protocol procedures.
8. Inability to collect all the patient's data used for evaluation of the study endpoints (e.g. lack of records in source documents required for verification of inclusion/exclusion criteria, safety and efficacy criteria).
9. Any other protocol deviations covered by the term “major deviation”.

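### The withdrawal list does not separate stopping treatment from stopping follow-up, so progression after an early exit goes unobserved, and the supplied text gives no rule for counting these patients in the Full Analysis Set

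*Combined protocol and SAP*

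**What the plan says.** All places are in the combined protocol and SAP.

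- **Criteria for Withdrawal or Termination** is one undivided list of 12 items. It includes "The necessity to use medications not permitted in the study", "Patient's decision to withdraw early for lack of efficacy or other reasons", "Deviation from personal visit schedule by more than 1 day" and an adverse event that requires stopping the study drug. It does not say which items end dosing only and which end observation.
- **Study design**: "Patients with COVID-19 progression to more severe level as well as hospitalized patients are considered as reaching the study endpoints", and they then leave the study. The later contacts are by telephone: "Visits 2, 5 and 6 are phone surveys to determine the patient's condition, presence/absence of complaints".
- **Schedule of study procedures**: "Unscheduled visit will be performed in case of aggravation (based on EPD), at the investigator's discretion and in case of early withdrawal". That visit includes physical examination, thermometry, the 14-symptom score and pulse oximetry. On the study-completion row, the note reads "In case of early withdrawal the procedure may be carried out at Visits 1-5 or at uncheduled visit". No contact after that is described.
- **Samples**, on the FAS: "This sample includes all enrolled patients, except for those who met at least one of the following events". The three exclusions are an eligibility violation, no dose taken, and no data at all after dosing.
- **Footnote 4** (attached to the deviation list under Samples) is the only text on incomplete primary-endpoint data. It decides eligibility for the per-protocol analysis.
- **Primary endpoint**: the frequency of progression by Day 28, tested as an odds ratio. Treatment lasts 5 days.

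**The concern.** Dosing ends on Day 5, but the endpoint is read on Day 28. A patient who leaves at about Day 6 without having progressed has some 22 days of endpoint time (28 − 6) that nobody is scheduled to observe. If dosed and eligible with any post-dose record, that patient is still in the FAS, and somebody must decide whether to count a non-event, count an event, impute or drop.

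Needing non-permitted medication and leaving for lack of efficacy are both plausibly linked to worsening, so the missing outcomes may be related to the endpoint. The off-schedule criterion discards follow-up for a purely logistical reason. At stake are the size of the estimated effect, the power, and the freedom to choose a counting rule after the data are known.

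**Working it through.** **Inputs.** Evaluation of sample size and the primary-endpoint hypotheses: placebo rate 0.15, odds ratio (OR) 0.5, alpha 0.04, power 0.80, likelihood-ratio chi-square, two-sided, 1:1. Number of patients: 798 randomised, 712 completing.

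**1. Reproduce the plan.** Raphamin odds = 0.5 × 0.15/0.85 = 0.0882, so the Raphamin rate is 0.0882/1.0882 = 0.0811. With H(p) = −p ln p − (1−p) ln(1−p) and d = 2[H(p̄) − ½H(p₁) − ½H(p₂)], power = Φ(√(2nd) − z₀.₉₈). At n = 356 per arm this is 0.800, so 712 reproduces; at 399 per arm it is 0.844. Inflation: 712/0.85 = 838.

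**2. Expected non-completers.** 798 − 712 = 86, or 10.8%, about 43 per arm. This is a planning expectation. It includes PCR-negative withdrawals and patients outside the FAS, and the plan words its allowance as at least 15% of those consenting, so it is not an upper bound.

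**3. What the missing rule leaves open.** Assume 43 unobserved per arm of 399, with completers at the design rates (53.4 and 28.9 events in 356).

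| Rule for leavers | Placebo | Raphamin | OR | Power, alpha 0.04 |
|---|---|---|---|---|
| All non-events | 53.4/399 = 13.4% | 28.9/399 = 7.2% | 0.505 | 0.795 |
| All events | 96.4/399 = 24.2% | 71.9/399 = 18.0% | 0.69 | 0.53 |

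For 20 to 60 unobserved per arm, power runs from 0.82 to 0.77 under the first rule and from 0.68 to 0.45 under the second. The second rule is an extreme.

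**4. Loss related to outcome.** Assume all 43 leavers in each arm are dropped (356 remain). A fraction f of one arm's would-be progressors is among its leavers; the other arm's leavers progress at the design rate. Where the affected arm has a true rate of 0.15, its observed rate is (1 − f) × 0.15 × 399/356. Rejection probability uses the Pearson chi-square with a normal approximation: Φ((δ − z·s₀)/s₁) + Φ((−δ − z·s₀)/s₁), where δ is the absolute rate difference and s₀, s₁ are its pooled and unpooled standard errors.

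- f = 10%: 5.99 of 43 leavers (14%) would progress, close to the 15% base rate. Observed rate 53.87/356 = 15.13%.
- f = 20%: 11.97 of 43 (28%). Observed rate 47.88/356 = 13.45%.

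| Scenario | f = 10% | f = 20% |
|---|---|---|
| No effect, loss in Raphamin arm: rejection at two-sided 5% | 5.0%, OR 1.01 | 9.1%, OR 0.88 |
| True OR 0.5, loss in placebo arm: power at alpha 0.04 | 81%, OR 0.49 | 60%, OR 0.57 |

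The reference power at 356 per arm with outcome-unrelated loss is about 80%. Simulation of the same scenarios agrees with the table.

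**The case against.** Much of the case against this point stands.

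- **Exit status is examined.** Moderate disease, as defined in the severity footnote, includes temperature above 38.0°C or SpO₂ below 95%, and both are measured at the unscheduled visit. A patient leaving because of worsening may already qualify as progressed and be counted. A reader might infer that worsening patients simply vanish from the endpoint; the documents do not support that. Only progression after exit is lost.
- **Sample size already absorbs neutral loss.** The plan needs 356 per arm, so losing 43 per arm at random costs nothing against the 80% target.
- **A false-positive reading is weak.** A reader might infer that the design inflates type I error. The trial is double-blind, with a placebo of the same regimen, excipients and description. With no drug effect there is no evident reason for arms to lose different patients, and equal loss keeps the error rate nominal.
- **Larger distortions can be computed, but only by an inconsistent construction.** Dropping only the would-be progressors of one arm, while treating every other leaver as fully observed, gives 18.8% rejection or 46.9% power at f = 20%. That conflicts with the plan's own expectation of about 43 non-completers in each arm.
- **Survival methods are named.** Non-parametric criteria lists survival analysis for repeated event data, and time to progression is an additional endpoint. Neither is assigned to the primary odds-ratio comparison, and no censoring rule is given.
- **The text is a protocol summary.** A reader might infer that no counting rule exists anywhere. The supplied text cannot show that; a fuller protocol may contain one.

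None of this supplies post-exit observation or an FAS rule in the text at hand.

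**Conclusion.** The gap is real and worth closing, but its size is moderate and conditional. As written, the plan ends observation for reasons that can be related to the endpoint, keeps the dosed and eligible patients concerned in the FAS if they have any post-dose data, and does not say how their unknown Day-28 status counts.

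Under outcome-unrelated, equal loss, or when leavers progress at roughly the design rate, there is essentially no distortion. It takes about 12 would-be progressors among 43 leavers in one arm to do visible damage: power of about 60% instead of about 80% if the arm is placebo and the true OR is 0.5, or about 9% rejection at a nominal 5% if the arm is Raphamin and there is no effect. The first direction is the more plausible, because a working drug would leave more worsening patients on placebo; the bias would then hide a real effect. The documents give no event rate among leavers, no split by arm and no count of those who would be in the FAS, so these figures are assumed scenarios, not predictions.

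**What to change.** 1. In Criteria for Withdrawal or Termination, separate stopping study treatment from stopping follow-up. Dosed, PCR-positive patients who stop early are still contacted at the existing Day 21 and Day 28 telephone visits, unless they refuse, about hospitalisation and physician-documented progression. These events count in the FAS primary analysis.
2. Record a visit more than 1 day off schedule as a protocol deviation that does not end follow-up.
3. Before unblinding, fix one FAS rule for Day-28 status that is still unknown, with at least one sensitivity analysis under a different assumption. The choice is the sponsor's. Multiple imputation within arm, using age group and vaccination history (which footnote 6 already requires the primary analysis to account for), is one reasonable option. If the full protocol already has a rule, cite it.

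Nothing here changes when treatment stops or when other medication is given.

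**Cost.** Protocol and SAP wording, about two calls per leaver (roughly 2 × 86 = 172 calls on the planning figure), and requests for treating-physician records where progression is reported. Telephone contact ascertains progression less completely than examination, some patients will refuse, and some outcomes will be recorded after non-study medication.

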### **Number of patients**

It is planned to include 838 patients, 798 of them will be randomized which is expected to yield at least 712 patients (356 per Raphamin and Placebo groups) completing all the protocol procedures.

### **Interim analysis**

The protocol does not schedule unblinded interim analyses. At the sponsor's decision, blinded interim analysis may be carried out to specify population parameters and potential further specification of sample size (increase only).

### **Treatment**

#### ***Group 1***

**Name of the medicinal product:** Raphamin

**Active ingredient:** affinity purified antibodies to human interferon-gamma – 10 000 UMA\*,  
affinity purified antibodies to CD4 – 10 000 UMA,  
affinity purified antibodies to  $\beta$ 2-microglobulin major histocompatibility complex class I – 10 000 UMA,  
affinity purified antibodies to  $\beta$ 1-domain of major histocompatibility complex class II – 10 000 UMA

\* *UMA – Units of Modifying Activity.*

**Excipients:** lactose monohydrate, microcrystalline cellulose, magnesium stearate

**Method of administration:** Per os without food. The tablet should be held in mouth until completely dissolved. On the first day of treatment, take 8 tablets according to the following scheme: 1 tablet every 30 minutes for the first 2 hours (total 5 tablets in 2 hours), then during the same day take another 1 tablet 3 times at equal intervals. On the 2nd day and beyond, take 1 tablet 3 times a day. The duration of treatment is 5 days.

**Dosage form:** Tablet for oral use.

**Description:** Flat, cylinder-shaped, scored beveled edge, white to off-white tablets.

**Storage conditions:** At temperature below 25°C. Keep out of the reach of children.

## ***Group 2***

**Name of the medicinal product:** Placebo

**Active ingredient:** N/A

**Excipients:** lactose monohydrate, microcrystalline cellulose, magnesium stearate

**Method of administration:** Per os without food. The tablet should be held in mouth until completely dissolved. On the first day of treatment, take 8 tablets according to the following scheme: 1 tablet every 30 minutes for the first 2 hours (total 5 tablets in 2 hours), then during the same day take another 1 tablet 3 times at equal intervals. On the 2nd day and beyond, take 1 tablet 3 times a day. The duration of treatment is 5 days.

**Dosage form:** Tablet for oral use.

**Description:** Flat, cylinder-shaped, scored beveled edge, white to off-white tablets.

**Storage conditions:** At temperature below 25°C. Keep out of the reach of children.

### ***Treatment duration***

Raphamin/Placebo treatment duration is 5 days.

### ***Observation period***

Overall, the patient will be monitored for 28 days (screening, randomization - up to 1 day, treatment - 5 days, follow-up - up to 28 days).

### ***Symptomatic (Standard) treatment***

Throughout the study the patients may receive an antipyretic medication Paracetamol (provided by the sponsor) and other symptomatic medications (vasoconstrictive nasal agents, antitussive agents).

### ***Dosage regimens***

Paracetamol (at body temperature  $\geq 38.0$  °C)

Orally, with plenty of liquid, 1-2 hours after eating.

Single dose is 500 (1 tablet). The maximum single dose is 1 g (2 tablets). The maximum daily dose is 4 g (8 tablets). The interval between doses is at least 4 hours. The patient should record thermometry values in EPD before taking the antipyretic drug, its name and dose.

[figure not shown]
### ***Prohibited concomitant therapy***

Four weeks prior to the enrollment as well as during the study (from signing of the patient information sheet and initiation of screening) the following medications are not allowed (ATC index is indicated in brackets):

1. Antiviral drugs (J05), as well as remdesivir, synthetic small interfering ribonucleic acid (siRNA) [double-stranded] (MIR 19), molnupiravir, nirmatrelvir + ritonavir, recombinant monoclonal antibodies (including sotrovimab, regdanvimab, bamlanivimab + etesivimab; casirivimab + imdevimab).
2. Systemic antimicrobial agents (J01).
3. Immunostimulants, including:
  - interferon inducers (acridonoacetic acid, meglumine acridone acetate/cycloferon, umifenovir/arbidol, kagocel, tiloron/amixin, polyadenyl acid + polyuridylic acid/poludan, sodium oxodihydroacridinyl acetate/neovir, lavomax, tilaxin, etc.);
  - interferons including recombinant interferon-alpha;
  - bacterial immunomodulators (including ribomunyl, sodium ribonucleate/ridostin, etc., sodium deoxyribonucleate/derinat, etc., IRS-19, imudon, broncho-munal, etc.);
  - pidotimod/immunorix;
  - interleukins;
  - synthetic immunostimulants (levamisole, alpha-glutamyl-tryptophan/thymogen, etc.);
  - medications containing thymus hormones.
4. Preventive anti-inflammatory therapy of COVID-19 including baricitinib, tofacitinib, netakimab, olokizumab, levilimab, tocilizumab, sarilumab, canakinumab, anakinra, methylprednisolone, dexamethasone, hydrocortisone.
5. Homeopathic medicines for the treatment of acute respiratory tract infections.
6. Systemic (oral or parenteral) corticosteroids.
7. Immunosuppressants (L04) including anakinra.
8. Antineoplastic agents (L01) and antineoplastic hormonal agents (L02).
9. Immune sera and immunoglobulins (J06) including anti-COVID plasma, human immunoglobulin against COVID-19.
10. Vaccines (J07).
11. Any unauthorised medicinal product.
12. Drugs that previously caused hypersensitivity/ allergic reactions in patient.

